As a result of the Article 20 benefit-risk reassessment, the MAH will additionally evaluate HCPs' compliance with the new PRAC recommendations and limitations for use to minimise the risk of VTE across all approved indications (i.e., tofacitinib should be used with caution in patients with known VTE risk factors regardless of indication and dosage), with additional focus on the use of tofacitinib 10 mg BID as a maintenance treatment for patients with UC, and use and prior treatments among patients aged 65 years and older treated with tofacitinib. The MAH will also examine tofacitinib prescribing patterns over time, as well as changes in the utilisation of tofacitinib among patients with VTE risk factors and among elderly patients aged  $\geq 65$  years following the updated recommendations and limitations for use. As a result of the 2021 signal evaluation procedure, the MAH will also assess HCPs' compliance with the new EMA recommendations and limitations for use related to tofacitinib use in patients with CV risk factors and use in patients with malignancy risk factors.b The MAH will also examine tofacitinib prescribing patterns over time in the 2021 signal evaluation procedure.

This protocol describes the drug utilisation study (i.e., component 2 described above). Data from this study, together with the findings from the tofacitinib prescriber survey (A3921334), will be used to assess whether the aRMM materials are effective. This non-interventional (NI) study is designated as a Post-Authorisation Safety Study (PASS) and is conducted by the MAH as a Category 3 commitment to the EMA.

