### 8. RESEARCH QUESTION AND OBJECTIVES

The research question is: Is there evidence that prescribers in the EU are compliant with the recommendations and limitations for use described in the tofacitinib aRMM materials?

The primary objectives are to:

- 1. Describe the characteristics of patients treated with tofacitinib, stratified by study country (i.e., Sweden, Hungary, the Netherlands, and Germany) and indication (i.e., RA, PsA, and UC; off-label indications), in terms of:
  - Demographics (e.g., age, sex); and
  - Comorbidities and prior and current medication use.

<sup>b The 2021 signal evaluation procedure also required the evaluation of tofacitinib use in elderly patients aged  $\geq$ 65 years, however, this assessment had already been added to the protocol following the findings from the 2019 Article 20 referral.

- 2. Evaluate prescribers' adherence to the tofacitinib aRMMs, specifically:
  - Compliance to the recommended posology per indication (average daily dose [ADD]) and duration of use;
  - Compliance to patient screening and laboratory monitoring prior to and during tofacitinib treatment; and
  - Compliance to recommendations for limitations of use, including:
    - Use in patients with VTE risk factors;
    - Use in patients aged 65 years and older;
    - Use in patients with CV risk factors;
    - Use in patients with malignancy risk factors;
    - Contraindicated use; and
    - Use with concomitant medications not compatible with tofacitinib.

The secondary objectives are to:

- 1. Describe prescribing patterns over time; and
- 2. Describe changes in the utilisation of tofacitinib following the updated recommendations and limitations for use implemented after the 2019 Article 20 referral and the 2021 signal evaluation procedure, specifically:
  - Use in patients with VTE risk factors;
  - Use in the elderly (patients aged 65 years and older);
  - Use in patients with CV risk factors; and
  - Use in patients with malignancy risk factors.

**Note:** In Gesetzliche Krankenversicherung (GKV) claims (Germany), outpatient diagnoses are reported quarterly, which could result in the misclassification of baseline clinical characteristics and select outcomes of interest, impacting all objectives except for primary objective 2.

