#### Figure 1. Overview of the study observation period

### 9.2.1. VTE Reporting Periods

A 105-month **observation period** will begin 01 April 2016 and end 31 December 2024. An 81-month **indexing period** will begin 01 April 2017 (i.e., the earliest date of the full distribution of the original aRMM materials for a country and indication [Sweden, RA]), end 31 December 2023, and be used to identify patients with  $\geq$ 1 tofacitinib prescription dispensing. Additionally, for some analyses, the indexing period will be split into the following 3 periods:

• **Reporting Period 1**, which will cover the up-to-26-month period after the initial distribution of the aRMM materials but *prior to* the PRAC/CHMP's notification of an increased risk of VTE among patients already at high risk (01 April 2017 through 31 May 2019, to allow for dissemination of DHPC letters following announcement of the provisional measures);

**Note:** Hungary will not have a **Reporting Period 1** because it received full reimbursement for RA in May 2019 and has yet to receive full reimbursement for PsA and UC (anticipated Q1 2023).

• **Reporting Period 2**, which will cover the 16-month period of and after the PRAC/CHMP's notification of an increased risk of VTE and mortality, through initial distribution and uptake of the 2019 Article 20 referral aRMM materials (1 June 2019 through 30 September 2020); and

**Note:** Hungary will not have a **Reporting Period 2** for PsA and UC because the September 2020 distribution date for the 2019 Article 20 referral aRMM materials in Hungary occurred prior to PsA and UC receiving full reimbursement (anticipated Q1 2023). Additionally, **Reporting Period 2** for RA in Hungary will only allow for <1 month of uptake of the 2019 Article 20 referral aRMM materials (which were distributed starting September 2020), in comparison to the approximate 6-7 month uptake of the

2019 Article 20 referral aRMM materials allowed for Sweden (which were distributed starting March 2020).

• **Reporting Period 3,** which will cover the 39-month period *after* the period of initial distribution and uptake of the 2019 Article 20 referral aRMM materials (1 October 2020 through 31 December 2023).

See Figure 2 for an overview of the VTE Reporting Periods 1-3.

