  - The proportion of patients with evidence of ≥1 malignancy risk factors *prior to* initiation of tofacitinib and no prior use of an alternative therapy (i.e., biologic), reported overall and by approved indication;
  - The proportion of patients who discontinue tofacitinib after developing ≥1 malignancy risk factor while taking tofacitinib; and
  - The proportion of patients who continue taking tofacitinib after developing ≥1 malignancy risk factor while taking tofacitinib;

- Contraindicated use, as measured by:e
  - A patient *initiating* tofacitinib therapy if they have severe hepatic impairment;i
  - A woman *initiating* tofacitinib therapy if she is pregnant;
  - A patient *initiating* tofacitinib therapy if they have or have had TB in the prior 2 months;
  - A patient initiating tofacitinib therapy if they have or have had a serious and/or opportunistic infection in the prior 2 months; and
  - A woman *receiving* tofacitinib therapy during her pregnancy;
- Use with concomitant medications not compatible with tofacitinib, as measured by:
  - The proportion of patients receiving biologics and/or potent immunosuppressants *while taking* tofacitinib; and
  - The proportion of patients receiving a live vaccination *while taking* tofacitinib;j

The secondary outcomes of interest will be:

- Tofacitinib prescribing patterns over time;e,f and
- Changes in the prescribing patterns (utilisation) of tofacitinib following the updated recommendations and limitations for use implemented after the 2019 Article 20 referral and the 2021 signal evaluation procedure, specifically:
  - Use in patients with VTE risk factors, as measured by:e,f
    - The proportion of patients with evidence of ≥1 VTE risk factors *prior to* initiation of tofacitinib, reported overall and by approved indication and stratified by VTE Reporting Periodk

<sup>i The data sources are unable to reliably ascertain severity of hepatic impairment; thus, this sub-outcome may be overestimated.

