#### 9.7.1.2.2.1.6. Use with concomitant medications not compatible with tofacitinib

The proportion of tofacitinib patients with concomitant use of medications not compatible with tofacitinib will be reported overall and by patients with and without  $\geq 2$  tofacitinib prescription dispensings.ss Additionally, the number of overlapping days' supply of the biologic or selected potent immunosuppressant with the tofacitinib prescription dispensing will be described continuously and categorically (e.g., 1-7 days, 8-14 days, 15-21 days, 22-30 days,  $\geq 31$  days; final cut-offs to be determined after examining the distribution of the data).

9.7.1.3. Secondary Objectives 1 and 2: Describe prescribing patterns; and Describe changes in tofacitinib prescribing patterns (utilisation) following the updated recommendations and limitations for use implemented after the 2019 Article 20 referral and the 2021 signal evaluation procedurett,uu,vv,ww

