### 9.9. Limitations of the research methods

This study uses large real-world data sources in Sweden, Hungary, the Netherlands, and Germany to describe utilisation of tofacitinib and prescriber adherence to related screening and monitoring guidelines. These data sources are large and representative of patient and physician populations in their respective countries. Given the late introduction of the 2019 Article 20 referral and 2021 signal evaluation procedure aRMM materials, the study is uniquely positioned to describe use patterns before and after the revised guidelines were instituted.

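### Secondary Objective 1 has no calendar-time measure of its own, and one average before each notification cannot reliably separate an earlier trend from a change at the regulatory action

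*Protocol*

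**What the plan says.** Section 8 of the protocol makes the description of prescribing over time a secondary objective in its own right. It is separate from the second objective, on changes after the 2019 referral and the 2021 signal procedure. In section 9.3.1 the first objective appears only as "Tofacitinib prescribing patterns over time", with footnotes on German quarterly diagnoses and on average daily dose. Every item under the second objective has a list of measures; this one has none. Table 3 and section 9.7.1.3 then place both objectives under one joint heading. The subsections below it cover VTE risk factors, age 65 and over, CV risk factors and malignancy risk factors, each by reporting period.

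The calendar axis is fixed in sections 9.2.1 and 9.2.2, where for some analyses "the indexing period will be split into the following 3 periods". VTE Period 1 is "01 April 2017 through 31 May 2019, to allow for dissemination of DHPC letters following announcement of the provisional measures"; Period 2 is "1 June 2019 through 30 September 2020"; Period 3 runs from October 2020 to December 2023. CV and malignancy Period 1 runs from April 2017 to June 2021. Period 2 starts in July 2021 and lasts 9 to 12 months. Period 3 takes the remaining 21 to 18 months.

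Section 9.7.1 rules out comparative statistical analyses. Section 7 nevertheless says that the data, taken with the prescriber survey, "will be used to assess whether the aRMM materials are effective", and section 9.9 calls the study "uniquely positioned to describe use patterns before and after the revised guidelines were instituted".

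**The concern.** An average over 26 or 51 months has a level but no slope. If the share of initiators with a risk factor was already falling before notification, Period 1 cannot show it, and the later, lower averages can be read as a response to the materials.

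The fixed periods also overlap with the other action. The restriction on use at age 65 and over was approved on 31 January 2020 (section 7), inside CV and malignancy Period 1, and Table 3 counts age 65 and over as both a CV and a malignancy risk factor. VTE Period 3 in turn contains the whole 2021 action. Diabetes, hypertension, malignancy and MI appear, with some differences in definition, in both the VTE list and the CV or malignancy lists.

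Shares among initiators are also blind to volume. If initiation fell equally in patients with and without a risk factor, no planned share would move. Counts per period would, but the periods differ in length, and no count of all initiators per calendar unit is planned.

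At stake is the before-and-after reading that feeds the judgement on the risk minimisation materials. Section 9.5.1 expects the treatment landscape to change during the study, but treats this only as a threat to sample size. The caveat in section 9.9 covers a share that does not decline; it does not cover a decline already under way.

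**Working it through.** **1. The plan's own period lengths.** Counted in inclusive calendar months, they reproduce: indexing period 81; VTE periods 26 + 16 + 39 = 81; CV and malignancy periods 51 + 9 + 21 = 81, or 51 + 12 + 18 = 81.

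**2. Midpoints, in months from 1 April 2017.**
- VTE: Period 1, 26/2 = 13; Period 2, 26 + 16/2 = 34; Period 3, 42 + 39/2 = 61.5.
- CV and malignancy: Period 1, 51/2 = 25.5; Period 3, 60 + 21/2 = 70.5 or 63 + 18/2 = 72.

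**3. Distance between Periods 1 and 3.**
- VTE: 61.5 − 13 = 48.5 months = 4.04 years.
- CV and malignancy: 45 to 46.5 months = 3.75 to 3.88 years.
- Consecutive periods are closer, 1.25 to 2.62 years.
- Where an indication starts later the gap shrinks. For UC in Sweden, from September 2018, it is 3.33 years (VTE) and 3.04 to 3.17 years (CV).

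**4. Overlap with the other action.**
- CV and malignancy Period 1: February 2020 to June 2021 is 11 + 6 = 17 months, and 17/51 = one third of the period follows approval of the age restriction.
- VTE Period 3: July 2021 to December 2023 is 9 + 21 = 30 months, and 30/39 = 77% of the period follows the end of CV and malignancy Period 1.

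**5. Size of a spurious difference (illustration).** Assume a steady fall in a share, no effect of any material, and uniform initiation. The documents give no drift rate, so a range is shown. The Period 1 to Period 3 difference is the drift rate times the gap in years.

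| Assumed drift (points a year) | VTE | CV and malignancy |
|---|---|---|
| 1 | 4.0 | 3.8 to 3.9 |
| 2 | 8.1 | 7.5 to 7.8 |
| 3 | 12.1 | 11.2 to 11.6 |

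Initiation need not be uniform: annual Swedish patient numbers in Table 7 rise from 336 to 889 to 1912. With two other assumed uptake shapes (linear growth, and a rise followed by a fall), a drift of 2 points a year gives 6.4 to 7.8 points (VTE) and 5.8 to 6.6 points (CV).

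**6. What Period 2 adds.** At 2 points a year, the VTE drift is 1.75 × 2 = 3.5 points from Period 1 to 2 and 2.29 × 2 = 4.6 points from Period 2 to 3. A clean step at notification would put the whole fall between Periods 1 and 2. A gradual response would spread it over both, as drift does.

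**7. What calendar unit the data can bear.** The indexing period holds 81/3 = 27 quarters or 81/6 = 13.5 half-years. A cell at the 100-patient minimum has about 100/27 = 3.7 initiators a quarter or 100/13.5 = 7.4 a half-year, too few for a quarterly series. German RA has 843 patients for 2017–2019 (Table 10). Spread evenly over the 33 months from April 2017, that is 843/11 = about 77 a quarter before the eligibility criteria are applied.

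**The case against.** The strongest reply is that section 9.7 leaves detailed methodology to the SAP, and that the calendar unit of a descriptive table belongs there. That is fair for the unit. It does not cover an objective with no stated measure in a protocol that defines the measures for the other secondary objective and fixes the reporting periods as its only calendar axis.

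Several stronger readings are not supported:
- A reader might infer that no counts will be reported. Section 9.7.1 promises frequency distributions, which imply numbers per period, and section 9.9 promises the number as well as the proportion of patients with VTE risk factors before and after the 2019 materials. Initiators per month could be derived from period totals, but only as another period average.
- A reader might infer that every outcome rests on three averages. The outcomes in patients aged 65 and over are tabulated over both sets of periods (section 9.7.1.3.2), which gives six overlapping windows and some view of the trend before 2021. Average daily dose is also split by reporting period, in the countries where it can be estimated. The interim reports add data cuts at the end of 2020 and 2022.
- A reader might infer that drift and a step look identical. Period 2 carries some information on shape, as step 6 shows.
- A reader might infer that the plan itself claims an effect. It disclaims comparative analysis and combines the results with a survey. The risk lies in interpretation.

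It also stands that a 27-quarter series would be unreadable in small cells, and that Hungary has no earlier periods for PsA and UC.

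**Conclusion.** The point holds in limited form and should be fixed. Secondary Objective 1 has no measure of its own. Section 9.7.1.3 reports risk-group results only by reporting period, and the single average before each notification cannot reliably distinguish an earlier trend from a change at the action. The mixing of the 2019 and 2021 actions within CV and malignancy Period 1 and VTE Period 3 follows from the protocol's own dates and needs no assumption.

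The 4-to-12-point figure does rest on assumptions: a linear drift of 1 to 3 points a year, uniform initiation and no effect of the materials. It shows how large a misleading difference could be; it does not predict one. The gap of about four years applies to Period 1 against Period 3 only, and is shorter for indications that started later.

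**What to change.** In section 9.7.1.3, state as the measure for Secondary Objective 1 a descriptive series by calendar time of index date, per country and by indication where counts allow:
- **Unit:** quarterly for large cells such as RA in Sweden or Germany; half-yearly or yearly elsewhere; small cells masked.
- **Content:** the number of initiators; the number and share aged 65 and over; and the number and share with at least one VTE, CV or malignancy risk factor, each with and without a prior biologic.
- **Markers:** the notification dates and the distribution dates in Table 2.
- **Use:** read the period results beside the series, without formal testing, so the descriptive character of the study is kept.

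Add to section 9.9 that a decline between periods may reflect a trend that began before the action.

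The cost is one further set of descriptive tables or figures from index dates and variables already planned, with no new data. The downside is imprecise or masked points in small cells, where the series may show little.

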### 9.3.2. Variable definitions

Table 3 summarises and defines the study variables to be collected and analysed in the selected databases. Unless otherwise specified, these variables will be assessed during each patient's entire study period, baseline period, and follow-up period.

This study will use code-based algorithms from the literature (validated against a gold standard measure, where possible) and/or other code lists to identify study variables. All code-based algorithms and code lists will be reviewed and/or approved by the study sponsor

prior to study initiation. Preliminary algorithms and/or codes are proposed in the following table (see also ANNEX 3 through ANNEX 7). Final algorithms and/or code lists will be refined as part of the SAP development.

Where possible, operational definitions for the variables listed in Table 3 will be similar across the databases. Only ICD-10 diagnosis codes and procedure codes are referenced in Table 3; the specific coding systems used in each data source will be further described in the SAP. See Section 9.4 (Data sources) for a description of the selected databases and Section 9.9 (Limitations of the research methods) for a summary of the limitations associated with these databases.

Variable	Role	Operational definition		
Indication m				
Indication n	Indication (including potential off-label indications)	Reported in the following categories: RA, PsA, UC, and Other / unknown (i.e., potential off-label indications).		
		Defined as $\geq 1$ International Classification of Disease, 10 th Revision (ICD-10) diagnosis code for RA, PsA, or UC in the 12 months prior to and including the day of tofacitinib initiation. If there is no ICD-10 diagnosis code in the patient's data for RA, PsA, or UC during this time period, then the indication will be reported as Other / unknown. If a patient has multiple codes for any combination of indications (e.g., RA and PsA), the ICD-10 diagnosis code closest to the index tofacitinib prescription dispensing will be used to determine indication.		
Primary Objective 1: Demo	Primary Objective 1: Demographics, comorbidities, and prior and current medications m			
Age at tofacitinib initiation	Demographic	Calculated as the date of tofacitinib initiation minus the patient's year of birth and reported in the following categories: <18 years, 18-29 years, 30-39 years; 40- 49 years; 50-59 years; 60-69 years; 70-79 years; and $\geq$ 80 years; and <65 years and $\geq$ 65 years.		
Sex	Demographic	Reported in the following categories: Male, Female, and Unknown. Assessed on the date of the index tofacitinib prescription dispensing.		

 Table 3.
 Operational definitions of study variables in the selected databases

m In GKV claims, outpatient diagnoses are reported quarterly.

n In the PHARMO Database Network, the high-budget impact medication dataset contains only declared medication for approved indications. It might not be possible to determine off-label use in this dataset.

Variable	Role	Operational definition
Hepatic impairment	Comorbidity	Defined as ≥1 ICD-10 diagnosis code for hepatic impairment.
Hepatic impairment, mild or moderate o	Comorbidity	Defined as ≥1 ICD-10 diagnosis code for mild or moderate hepatic impairment.
Hepatic impairment, severe o	Comorbidity	Defined as ≥1 ICD-10 diagnosis code for severe hepatic impairment.
Renal impairment	Comorbidity	Defined as ≥1 ICD-10 diagnosis code for renal impairment or a combination of ICD-10 diagnosis codes and/or ICD-10 procedure codes.
Renal impairment, mild o	Comorbidity	Defined as ≥1 ICD-10 diagnosis code for mild renal impairment or a combination of ICD-10 diagnosis codes and/or ICD- 10 procedure codes.
Renal impairment, moderate o	Comorbidity	Defined as ≥1 ICD-10 diagnosis code for moderate renal impairment or a combination of ICD-10 diagnosis codes and/or ICD-10 procedure codes.
Renal impairment, severe o	Comorbidity	Defined as ≥1 ICD-10 diagnosis code for severe renal impairment or a combination of ICD-10 diagnosis codes and/or ICD- 10 procedure codes.
Herpes zoster (HZ)	Comorbidity	Defined as $\geq 1$ ICD-10 diagnosis code for HZ.
Human immunodeficiency virus (HIV)	Comorbidity	Defined as ≥1 ICD-10 diagnosis code for HIV.
Tuberculosis (TB), including both active and latent TB p	Comorbidity	Defined as ≥1 ICD-10 diagnosis code for TB.
Viral hepatitis B or C	Comorbidity	Defined as ≥1 ICD-10 diagnosis code for viral hepatitis B or C.
Serious and opportunistic infections of interest (including HIV, HZ, TB, and viral hepatitis B and	Comorbidity	Defined as $\geq 1$ ICD-10 diagnosis code for a serious and/or opportunistic infection of interest.
C)		DIAGNOSIS CODES FOR SELECT INFECTIONS OF INTEREST.
Diverticulitis	Comorbidity	Defined as ≥1 ICD-10 diagnosis code for diverticulitis.

 Table 3.
 Operational definitions of study variables in the selected databases

° The data sources are unable to reliably ascertain severity of hepatic impairment and renal impairment.

<sup>p The data sources may not be able to differentiate between active and latent TB.

Variable	Role	Operational definition
Malignancy (non- metastatic and metastatic, excluding non-melanoma skin cancer)	Comorbidity	Defined as ≥1 ICD-10 diagnosis code for a malignancy (excluding non-melanoma skin cancer).
Non-melanoma skin cancer	Comorbidity	Defined as ≥1 ICD-10 diagnosis code for non-melanoma skin cancer.
Gastrointestinal perforation	Comorbidity	Defined as $\geq 1$ ICD-10 diagnosis code for gastrointestinal perforation.
Interstitial lung disease	Comorbidity	Defined as ≥1 ICD-10 diagnosis code for interstitial lung disease.
		Complete list in ANNEX 4. LIST OF DIAGNOSIS AND PROCEDURE CODES FOR INTERSTITIAL LUNG DISEASE.
Diabetes	Comorbidity	Defined as ≥1 ICD-10 diagnosis code for diabetes.
Immunodeficiencies of interest	Comorbidity	Defined as $\geq$ 1 ICD-10 diagnosis code for immunodeficiency.
		Complete list in ANNEX 5. LIST OF DIAGNOSIS CODES FOR SELECT IMMUNODEFICIENCIES OF INTEREST.
Prior use of corticosteroids	Medication history	Defined as ≥1 prescription dispensing of a corticosteroid (as identified by ATC code[s]) in the 12 months prior to the index tofacitinib dispensing.
		Complete list in ANNEX 7. LIST OF ATC CODES FOR COMEDICATIONS OF INTEREST.
Prior use of statins	Medication history	Defined as $\geq 1$ prescription dispensing of a statin (as identified by ATC code[s]) in the 12 months prior to the index tofacitinib dispensing.
		Complete list in ANNEX 7. LIST OF ATC CODES FOR COMEDICATIONS OF INTEREST.

 Table 3.
 Operational definitions of study variables in the selected databases

Variable	Role	Operational definition
Prior use of any biologic q	Medication history	Defined as ≥1 prescription dispensing of a biologic (as identified by ATC code[s]) in the 12 months prior to the index tofacitinib dispensing.
		Complete list in ANNEX 6. LIST OF ATC CODES FOR MEDICATIONS OF INTEREST TO AVOID WHILE TAKING TOFACITINIB.
Prior use of conventional synthetic DMARDs (csDMARDs)	Medication history	Defined as ≥1 prescription dispensing of a csDMARD (as identified by ATC code[s]) in the 12 months prior to the index tofacitinib dispensing.
		Complete list in ANNEX 6. LIST OF ATC CODES FOR MEDICATIONS OF INTEREST TO AVOID WHILE TAKING TOFACITINIB.
Prior use of methotrexate (MTX)	Medication history	Defined as $\geq 1$ prescription dispensing of MTX (as identified by ATC code L04AX03) in the 12 months prior to the index tofacitinib dispensing.
Prior use of anti-TB therapy	Medication history	Defined as $\geq 1$ prescription dispensing of anti-TB therapy (as identified by ATC code[s]) in the 12 months prior to the index tofacitinib dispensing.
Prior vaccination r	Medication history	Defined as $\geq 1$ procedure code and/or $\geq 1$ prescription dispensing (as identified by ATC code[s]) for a vaccination, overall and stratified by live and non-live vaccinations in the 12 months prior to the index tofacitinib dispensing.
		Complete list in ANNEX 7. LIST OF ATC CODES FOR COMEDICATIONS OF INTEREST.

Table 3.	Operational	definitions of	f study	variables in	the selected	databases

<sup>q Biologics that are dispensed or administered primarily through hospital channels may not captured (completely) in the data sources.

<sup>r This variable will not be assessed in Sweden because most vaccinations are not done in specialist care and therefore are not captured in the NPR, nor are vaccines prescribed and purchased by the patients in the pharmacies and therefore are not be captured in the PDR. Vaccination data are also unavailable in the PHARMO Database Network. In GKV claims, it is not possible to differentiate between live and non-live vaccines.

Variable	Role	Operational definition
Concomitant use of a contraindicated immunomodulator csDMARD	Comedication	Defined as ≥1 overlapping days' supply of a tofacitinib prescription dispensing and a prescription dispensing for a contraindicated immunomodulator csDMARD (as identified by ATC code[s]) during the follow-up period.
		Note: Concomitancy with a contraindicated csDMARD can occur even if the contraindicated medication is dispensed prior to the index tofacitinib dispensing, provided that there is $\geq 1$ overlapping days' supply with a tofacitinib prescription dispensing during the follow-up period.
		Duration of tofacitinib therapy defined in Section 9.3.3.
Concomitant use of MTX	Comedication	Defined as ≥1 overlapping days' supply of a tofacitinib prescription dispensing and a prescription dispensing for MTX (as identified by ATC code L04AX03) during the follow-up period.
		Note: Concomitancy with MTX can occur even if the medication is dispensed prior to the index tofacitinib dispensing, provided that there is $\geq 1$ overlapping days' supply with a tofacitinib prescription dispensing during the follow-up period.
		Duration of tofacitinib therapy defined in Section 9.3.3.
Concomitant use of a corticosteroid	Comedication	Defined as ≥1 overlapping days' supply of a tofacitinib prescription dispensing and a prescription dispensing for a corticosteroid (as identified by ATC code[s]) during the follow-up period.
		Note: Concomitancy with a corticosteroid can occur even if the medication is dispensed prior to the index tofacitinib dispensing, provided that there is $\geq 1$ overlapping days' supply with a tofacitinib prescription dispensing during the follow-up period.
		Duration of tofacitinib therapy defined in Section 9.3.3.

 Table 3.
 Operational definitions of study variables in the selected databases

Variable	Role	Operational definition	
Concomitant use of anti- TB therapy	Comedication	Defined as ≥1 overlapping days' supply of a tofacitinib prescription dispensing and a prescription dispensing for anti-TB therapy (as identified by ATC code[s]) during the follow-up period.	
		Note: Concomitancy with anti-TB therapy can occur even if the medication is dispensed prior to the index tofacitinib dispensing, provided that there is $\geq 1$ overlapping days' supply with a tofacitinib prescription dispensing during the follow-up period.	
		Duration of tofacitinib therapy defined in Section 9.3.3.	
Primary Objective 2: Prescribers' adherence to the tofacitinib aRMMs s			
Compliance to the recomm	ended posology per indication and o	luration of use t	
Duration of tofacitinib therapy	Utilisation	Defined in Section 9.3.3. Assessed during the follow-up period.	
Average daily dose (ADD) t	Outcome: Compliance to recommended posology	Defined in Section 9.3.4. Assessed during the follow-up period.	
A patient with an ADD of >11 mg during any of the 8-week follow-up intervals and no evidence of a diagnosis for UC t	Outcome: Compliance to recommended posology	Defined as 0 ICD-10 diagnosis codes for UC prior to and including the date of the first tofacitinib prescription dispensing in an 8-week follow-up interval that has an ADD of >11 mg (ADD defined in Section 9.3.4).	

1 able 5. Operational definitions of study variables in the selected databas	Table 3.	Operational definitions of stud	y variables in	the selected	database
--	----------	--	----------------	--------------	----------

<sup>s In GKV claims, outpatient diagnoses are reported quarterly.

<sup>t The study outcomes that contain an ADD component will *not* be assessed in Hungary or the Netherlands. The Hungarian administrative claims database is unable to estimate ADD, either directly or by proxy, due to how tofacitinib is captured in the database. In the high-budget impact medication dataset of the PHARMO Database Network, neither ADD nor the number of pills per prescription is captured.

Variable	Role	Operational definition	
A patient with an ADD of $\geq$ 15 mg in Weeks 16-23, Weeks 24-31, Weeks 32- 39, and/or Weeks 40-47 of follow-up with evidence of a diagnosis for UC but no use of an alternative therapy (i.e., biologic) prior to tofacitinib initiation t	Outcome: Compliance to recommended posology	Defined as ≥1 ICD-10 diagnosis codes for UC and ≥1 prescription dispensing for a biologic (as identified by ATC codes) prior to and including the date of the index tofacitinib prescription with an ADD ≥15 mg in Weeks 16-23, Weeks 24-31, Weeks 32-39, and/or Weeks 40- 47 of follow-up (ADD defined in Section 9.3.4). Complete list of biologics in ANNEX 6. LIST OF ATC CODES FOR MEDICATIONS OF INTEREST TO AVOID WHILE TAKING TOFACITINIB. Note: This definition will miss those who have 1 10-mg BID prescription and the remaining prescriptions are 5-mg BID.	
Compliance to patient screening and laboratory monitoring prior to and during tofacitinib treatment u			

 Table 3.
 Operational definitions of study variables in the selected databases

The following recommended screenings and monitoring will be assessed in the following timeframes:

- In the 30 days prior to and including the day of tofacitinib initiation;
- In the 31 to 60 days prior to tofacitinib initiation;
- In the 61 to 90 days prior to tofacitinib initiation;
- In the 91 to 180 days prior to tofacitinib initiation;

For patients with 6 months of tofacitinib therapy (duration of tofacitinib therapy defined in Section 9.3.3):

- In the 60 days after and including the day of tofacitinib initiation;
- In the 61 to 120 days after tofacitinib initiation; and
- In the 121 to 180 days after tofacitinib initiation.

For patients with 12 months of tofacitinib therapy (duration of tofacitinib therapy defined in Section 9.3.3):

- In the 181 to 240 days after tofacitinib initiation;
- In the 241 to 300 days after tofacitinib initiation; and
- In the 301 to 360 days after tofacitinib initiation.

For analyses, 1 month will be defined as 30 days and 1 year will be defined as 360 days.

Timeframes for the baseline period are mutually exclusive. For patients with multiple procedure and/or diagnosis codes during the baseline period, the procedure or diagnosis code occurring closest to the index tofacitinib prescription dispensing will be selected.

<sup>u This outcome (and all sub-outcomes) will *not* be assessed in Sweden because the Swedish national health registers do not capture the laboratory tests of interest. In GKV claims, it may not be possible to differentiate an ALC laboratory test from an ANC laboratory test, or an ALT laboratory test from an AST laboratory test. In the PHARMO Database Network, TB screening and viral hepatitis B and C testing are not captured.

Variable	Role	Operational definition		
Creatinine (serum or urine) laboratory testing	Outcome: Screening	Defined as $\geq 1$ procedure code or $\geq 1$ ICD- 10 diagnosis code for a creatinine (serum or urine) laboratory test.		
TB screening	Outcome: Screening	Defined as $\geq 1$ procedure code or $\geq 1$ ICD-		
	Outcome: Monitoring	10 diagnosis code for TB (active and latent) screening.		
Viral hepatitis B and C	Outcome: Screening	Defined as $\geq 1$ procedure code or $\geq 1$ ICD-		
screening	Outcome: Monitoring	and C screening.		
Absolute lymphocyte	Outcome: Screening	Defined as $\geq 1$ procedure code or $\geq 1$ ICD-		
count (ALC) laboratory testing	Outcome: Monitoring	10 diagnosis code for ALC laboratory testing.		
Absolute neutrophil count	Outcome: Screening	Defined as $\geq 1$ procedure code or $\geq 1$ ICD-		
(ANC) laboratory testing	Outcome: Monitoring	testing.		
Haemoglobin laboratory	Outcome: Screening	Defined as $\geq 1$ procedure code or $\geq 1$ ICD-		
	Outcome: Monitoring	lo diagnosis code for haemoglobin laboratory testing.		
Alanine aminotransferase	Outcome: Screening	Defined as $\geq 1$ procedure code or $\geq 1$ ICD- 10 diagnosis and for ALT and/or AST		
aminotransferase (AST) laboratory testing	Outcome: Monitoring	laboratory testing.		
Lipid panel (i.e., total cholesterol, HDL, LDL,	Outcome: Monitoring	Defined as ≥1 procedure code or ≥1 ICD- 10 diagnosis code for lipid panel		
and TG) laboratory testing		laboratory testing.		
		Note: The patient must have evidence of receiving all 4 laboratory tests that comprise a lipid panel.		
Compliance to recommendations for limitations of use in patients with VTE risk factors v				
Assessment of VTE risk factors prior to initiation of tofacitinib				
Prior VTE	Outcome: VTE risk factor	Defined as $\geq 1$ ICD-10 diagnosis code for		
		VTE in the 12 months prior to or on the day of the index tofacitinib dispensing.		
History of surgery, major	Outcome: VTE risk factor	Defined as $\geq 1$ procedure code for a major surgery in the 12 months prior to or or		
		the day of the index tofacitinib dispensing.		
Prior recent myocardial	Outcome: VTE risk factor	Defined as $\geq 1$ ICD-10 diagnosis code for		
infarction (MI)		an MI in the 3 months prior to or on the day of the index tofacitinib dispensing.		

Table 5. Operational definitions of study variables in the selected databases
---

<sup>v In GKV claims, outpatient diagnoses are reported quarterly.

Variable	Role	Operational definition
History of heart failure	Outcome: VTE risk factor	Defined as ≥1 ICD-10 diagnosis code for heart failure in the 12 months prior to or on the day of the index tofacitinib dispensing.
History of combined hormonal contraceptives or hormonal replacement therapy use	Outcome: VTE risk factor	Defined as ≥1 prescription dispensing of a combined hormonal contraceptives and/or hormonal replacement therapy (as identified by ATC codes) in the 12 months prior to or on the day of the index tofacitinib dispensing.
History of inherited coagulation disorder	Outcome: VTE risk factor	Defined as $\geq 1$ ICD-10 diagnosis code for inherited coagulation disorder in the 12 months prior to or on the day of the index tofacitinib dispensing.
